2.1 Sample size calculation

The sample size is determined to ensure a sufficient power for step 1 and step 2 in the hierarchical testing procedure for the primary estimand presented in section $\underline{2}$. The power for step 3 and 4 in the hierarchical testing procedure will also be presented. The sample size is determined using a non-inferiority limit of 0.4% in step 1, which was chosen as described in section 5.2.1 in the protocol. The statistical evaluation will be done as described in sections $\underline{2.3}$ and $\underline{2.4}$.

In previous confirmatory trials where faster aspart has been investigated, the completion rates have been high. Therefore it will be expected that treatment discontinuation might be as low as 10% where trial discontinuation constitutes half of these and with similar withdrawal reasons in the treatment arms.

Power for the non-inferiority step (Step 1) is based on a t-statistic under the assumption of a one-sided test of size 2.5% for the FAS. A mean treatment difference of -0.1% for the comparison between faster aspart and NovoRapid[®] in favour of faster aspart is expected. As trials in this population where data from treatment withdrawn subjects is retrieved is limited, a conservative estimate of the standard deviation (SD) in change from baseline in HbA_{1c} of 0.8% was chosen. The power for superiority in step 3 will be calculated using the same assumptions as for step 1 but without the non-inferiority margin.

For determination of power in step 2 in the hierarchical testing, where change from baseline in 1-hour PPG increment 16 weeks after randomisation is compared between faster aspart and NovoRapid® a t-statistic with a two-sided test of size 5% is used, where the treatment difference is

Statistical Analysis Plan		Date:	12 February 2019	Novo Nordisk
Trial ID: NN1218-4113	CONFIDENTIAL	Version:	2.0	
UTN: U1111-1180-0636	CONFIDENTIAL	Status:	Final	
EudraCT No.: 2016-000878-38		Page:	9 of 29	

expected to be at least 0.6 mmol/L [11 mg/dL]. The SD=3.5 mmol/L [63 mg/dL] in change from baseline in 1-hour PPG increments 16 weeks after randomisation based on laboratory analysed PG in a standardised meal test will be considered reasonable based on trials NN1218-3852 and NN1218-3853.

The power in step 4, where superiority of faster aspart over NovoRapid $^{\$}$ in change from baseline in 1,5-anhydroglucitol 16 weeks after randomisation is tested a t-statistic with a two-sided test of size 5% is used. The mean treatment difference is expected to be at least 0.2 μ g/mL and an SD of 3.5 μ g/mL will be used based on trials NN1218-3852 and NN1218-3853.

The power calculations are done using proc power in SAS 9.4. Please refer to Table 2–1 for assumptions for the sample size calculation.

Table 2–1 Specifications assumed for sample size calculation

Statistical test	Significance level	Analysis population	Non-inferiority margin	SD	Mean difference	Randomisation scheme
Step 1 2-group t-tes	t One-sided 2.5 %	FAS	0.4 % (absolute)	0.8 %	-0.1 %	1:1
Step 2 2-group t-tes	t Two-sided 5.0%	FAS	NA	3.5 mmol/L	0.6 mmol/L	1:1
Step 3 2-group t-tes	t Two-sided 5.0%	FAS	NA	0.8 %	-0.1 %	1:1
Step 4 2-group t-tes	t Two-sided 5.0%	FAS	NA	$3.5~\mu g/mL$	$0.2~\mu\text{g/mL}$	1:1

In Table 2–2 the sensitivity of the sample size to the power shown for three different sizes of FAS. Three different choices of the mean difference are used to calculate the power in step 2.

Table 2–2 Sensitivity of sample size to power

N total	N per arm	Step 1			Step 2			Step 3			Step 4		
FAS	FAS	Mean diff (%)	SD (%)	Power (%)	Mean diff (mmol/L)	SD (mmol/L)	Power (%)	Mean diff (%)		Power (%)	Mean diff (μg/mL)	SD (μg/mL)	Power (%)
		-0.1	0.8	>99.9	0.5	3.5	58.1	-0.1	0.8	47.4	0.2	3.5	13.9
920	460	-0.1	0.8	>99.9	0.6	3.5	73.8	-0.1	0.8	47.4	0.2	3.5	13.9
		-0.1	0.8	>99.9	0.7	3.5	85.8	-0.1	0.8	47.4	0.2	3.5	13.9
		-0.1	0.8	>99.9	0.5	3.5	64.7	-0.1	0.8	53.4	0.2	3.5	15.5
1072	536	-0.1	0.8	>99.9	0.6	3.5	80.1	-0.1	0.8	53.4	0.2	3.5	15.5
		-0.1	0.8	>99.9	0.7	3.5	90.5	-0.1	0.8	53.4	0.2	3.5	15.5
		-0.1	0.8	>99.9	0.5	3.5	70.4	-0.1	0.8	58.9	0.2	3.5	17.0
1224	612	-0.1	0.8	>99.9	0.6	3.5	85.0	-0.1	0.8	58.9	0.2	3.5	17.0
		-0.1	0.8	>99.9	0.7	3.5	93.8	-0.1	0.8	58.9	0.2	3.5	17.0

In conclusion, 1072 subjects in the FAS (536 subjects per group) will ensure a marginal power of >99.9% to show non-inferiority in step 1, given that the actual treatment difference is -0.1%, and a marginal power of 80.1% to show superiority in step 2, given that the actual treatment difference is 0.6 mmol/L.

Assuming a screening failure rate of 30% and run-in failure rate of 15%, 1803 subjects should be screened for inclusion in the trial.

2.2 **Definition of analysis sets**

The following analysis sets are defined in accordance with the ICH-E9 guidance $^{\perp}$.

 Full Analysis Set (FAS) includes all randomised subjects. In exceptional cases, randomised subjects may be excluded from the FAS. In such cases, the reason for exclusion will be justified and documented. Subjects in the FAS will contribute to the evaluation "as randomised"

- Per Protocol (PP) Analysis Set includes all subjects in the FAS, excluding subjects who:
 - Have violated any inclusion criteria
 - o Have fulfilled any exclusion criteria

Subjects in the PP analysis set will contribute to the evaluation "as treated"

• Safety Analysis Set includes all subjects receiving at least one dose of randomised treatment. Subjects in the safety analysis set will contribute to the evaluation "as treated".

Randomised subjects who are lost to follow-up, and where no exposure information of the trial product or its comparator is available after randomisation, will be handled as unexposed.

Before data are released for statistical review, a blinded review of all data will take place to identify serious non-adherence to the protocol that may potentially affect the results. Furthermore, extreme values and outliers will be identified by the statistician during programming and data review, according to ICH-E9¹. This will be performed using a fake randomisation.

The subjects or observations to be excluded, and the reasons for their exclusion must be documented and signed by those responsible before database lock. The subjects and observations excluded from analysis sets, and the reason for this, will be described in the clinical trial report.

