6.1 Number of subjects

Number of subjects planned to be screened: 1803

Number of subjects planned to be included in the run-in period: 1262

Number of subjects planned to be randomised: 1072

A screening failure rate of approximately 30% and a run-in failure rate of approximately 15% are anticipated for this trial.

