6.8 Subject replacement

Subjects who discontinue trial products prematurely or withdraw from trial will not be replaced.

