8.1.10 Withdrawal from trial

If a subject withdraws consent, the investigator must aim to undertake procedures similar to those for Visit 30 including the meal test, as soon as possible, also called Visit 30A. The investigator must encourage the subjects to undergo the meal test at Visit 30A. The meal test must be performed with bolus trial insulin according to randomisation. If it is not feasible due to safety reasons including

 Protocol
 Date:
 23 February 2018
 Novo Nordisk

 Trial ID: NN1218-4113
 Version:
 4.0
 4.0
 Status:
 Final
 Final
 Page:
 37 of 112
 37 of 112

pregnancy as judged by the investigator the meal test should be performed with the marketed bolus product the subject is switched to.

If the subject agrees, the investigator must aim to perform the follow up visits (FU1 and FU2) 7 and 30 days after discontinuation of trial product.

In case a premature discontinuation of trial product subject chooses to withdraw consent from trial after completing Visit 30A, FU1 and FU2, the investigator must encourage the subjects to undergo procedures of Visit 30, as soon as possible, whereas FU1 and FU2 are not to be completed again.

The end of treatment and end of trial form in the eCRF must be completed, and final drug accountability must be performed even if the subject is not able to come to the trial site. A treatment discontinuation session must be made in the IWRS. The case book must be signed.

Although a subject is not obliged to give his/her reason(s) for withdrawing consent, the investigator must make a reasonable effort to ascertain the reason(s), while fully respecting the subject's rights. Where the reasons are obtained, the primary reason for withdrawing consent must be specified in the eCRF.

A subject that is withdrawn from trial before the End of Treatment Visit (V30), will be considered to be a treatment non-completer and a trial non-completer.

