Subjects that prematurely discontinue from treatment or withdraw from trial will attend end of treatment visit called visit 30A. Data collected at this visit will be reallocated to the next scheduled visit where the given assessment is planned. As a general rule, all observed values from randomised subjects will be used in all statistical analyses, but in case two different values are associated to the same visit in time, the use of a given value will depend on the estimand of interest. For the primary estimand the reallocated on-treatment value will not be used and for the secondary estimand the reallocated on-treatment value will be used.

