As the second step of the hierarchical testing procedure change from baseline in 1-hour PPG increment (meal test) 16 weeks after randomisation will be tested for superiority of faster aspart compared to Novo Rapid[®].

The 1-hour PPG increment will be analysed based on the laboratory measured values in the meal test, and is derived as the 1-hour PPG measurement minus the pre-prandial PG measurement.

The 1-hour PPG increment endpoint will be analysed using the FAS and the in-trial observation period based on a multiple imputation technique where the change from baseline in 1-hour PPG increment at week 16 for subjects with missing value are imputed based on data from subjects in the NovoRapid® arm with non-missing values at week 16. Multiple copies (100 copies) of the full dataset will be generated by imputing missing values based on estimated parameters as follows:

- An analysis of variance model with region and metformin use at baseline (Yes/No) as factors and baseline 1-hour PPG increment as covariate is fitted to the change from baseline in 1-hour PPG increment at week 16 for the NovoRapid® group only. The estimated parameters, and their variances, from this model are used to impute missing values using stochastic simulation at week 16 for subjects in both treatment groups in order to generate 100 complete datasets.
- For each of the complete data sets, the change from baseline to week 16 is analysed using an analysis of variance model with treatment, region and metformin use at baseline (Yes/No) as factors, and baseline 1-hour PPG increment as covariate.
- The estimates and standard deviations for the 100 data sets are pooled to one estimate and associated standard deviation using Rubin's formula. From this, the pooled estimate and 95% confidence interval for the treatment difference are calculated.

The superiority will be assessed by comparing the upper limit of the 95% CI to 0. If the upper 95% CI is below 0 then superiority will be confirmed.

Change from baseline in HbA_{1c} 16 weeks after randomisation (step 3)

Step 3 in the hierarchical testing procedure is to confirm superiority of change from baseline HbA_{1c} 16 weeks after randomisation of the effect of treatment with faster aspart compared to NovoRapid[®]. Superiority will be addressed based on the same 95% CI that was used for addressing the primary

Statistical Analysis Plan		Date:	12 February 2019	Novo Nordisk
Trial ID: NN1218-4113	CONFIDENTIAL	Version:	2.0	

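### Does the 80.1% power for the 1-hour PPG increment need an allowance for discontinuation and for imputation from the NovoRapid arm?

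*SAP*

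**What the plan says.** SAP 2.1 says the sample size is chosen to give adequate power for steps 1 and 2 under the primary estimand. Table 2-1 names the FAS as the analysis population for every step. For step 2 the inputs are a two-group t-test, two-sided 5%, difference 0.6 mmol/L and SD of the change 3.5 mmol/L. The conclusion is a "marginal power of 80.1% to show superiority in step 2, given that the actual treatment difference is 0.6 mmol/L". Table 2-2 repeats the calculation for 920, 1072 and 1224 subjects and for differences of 0.5, 0.6 and 0.7.

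On losses after randomisation, the section says "it will be expected that treatment discontinuation might be as low as 10% where trial discontinuation constitutes half of these". Protocol 6.1 gives "Number of subjects planned to be randomised: 1072", the same number that is powered. Protocol 6.8 adds: "Subjects who discontinue trial products prematurely or withdraw from trial will not be replaced".

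The step 2 analysis in SAP 2.4.1 differs from the t-test in two ways. Week-16 changes "for subjects with missing value are imputed based on data from subjects in the" NovoRapid arm who have a week-16 value, whichever arm the subject is in. Each completed dataset is then analysed "using an analysis of variance model with treatment, region and metformin use at baseline (Yes/No) as factors, and baseline 1-hour PPG increment as covariate".

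Two further rules govern how much is missing. Under Protocol 8.1.10, a subject who withdraws consent is encouraged to attend Visit 30A for a meal test: "The meal test must be performed with bolus trial insulin according to randomisation", with an exception for safety. Under the visit reallocation rule in SAP section 2, "Data collected at this visit will be reallocated to the next scheduled visit where the given assessment is planned". The only post-baseline scheduled visit with a meal test is Visit 30.

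**The concern.** Step 2 is where the sample size binds. Step 1 has power above 99.9%, and step 2 sits just above 80%. The section states a discontinuation rate, phrased as a favourable case, and then does not use it. Only screening failure (30%) and run-in failure (15%) enter the numbers: 1803 × 0.70 × 0.85 = 1072.8.

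An imputed faster aspart subject takes a value from a model fitted to NovoRapid, so carries no treatment effect. A subject who stops trial drug but stays is meal-tested at Visit 30 on a marketed bolus (Protocol 8.3.1) and may also lose the advantage. If 0.6 mmol/L is the difference in subjects on drug, the difference the test sees is smaller and 80.1% is too high. The plan gives no derivation of 0.6 and does not say outright which difference it is.

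If the shortfall were real, the chance of passing step 2, and so of testing steps 3 and 4 at all, would be lower than a reader supposes. Similarly, the 53.4% and 15.5% for steps 3 and 4 are described as power within the hierarchical procedure, although each is computed as a stand-alone test.

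**Working it through.** **Inputs.** From SAP 2.1: 536 per arm, difference 0.6, SD 3.5, two-sided 5%; 10% stop treatment, of whom half (5%) leave the trial. From SAP 2.4.1: imputation from NovoRapid only, and adjustment for baseline increment. The correlation ρ between baseline and week-16 increment is not in the documents, so it is assumed and shown over a range.

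**1. The plan's figure.** Standard error = 3.5 × √(2/536) = 0.2138. Noncentrality = 0.6 / 0.2138 = 2.806. The noncentral t with 1070 degrees of freedom gives 80.06%, printed as 80.1%. All nine step 2 entries of Table 2-2 reproduce, as do the step 3 and step 4 columns.

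**2. Reading A: 0.6 is the primary-estimand difference.** With a share f imputed at zero effect, net difference = on-drug difference × (1 − f). For f = 0.05 and a net 0.6, the on-drug difference is 0.6 / 0.95 = 0.632. Imputation then costs only a small increase in variance. Simulating NovoRapid-only multiple imputation with Rubin's rules gives 79 to 80% across separate runs, unadjusted. Deleting the 5% instead (509 per arm) gives 78.0%, but deletion is not the planned analysis.

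**3. Reading B: 0.6 is the on-drug difference, unadjusted.**

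| Scenario | Net difference | Closed form | Simulated imputation |
|---|---|---|---|
| 5% imputed | 0.6 × 0.95 = 0.57 | 75.9% | about 75% |
| 5% imputed, further 5% off drug with no benefit | 0.6 × 0.90 = 0.54 | 71.3% | about 70% |

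**4. The planned baseline adjustment.** Assume equal variances at baseline and week 16. The variance of the change is 2σ²(1 − ρ), and the residual variance after adjustment is σ²(1 − ρ²). The ratio is (1 + ρ)/2, so the residual SD is 3.5 × √((1 + ρ)/2). At ρ = 0.7 this is 3.5 × √0.85 = 3.23; at ρ = 0.5 it is 3.5 × √0.75 = 3.03. The SD of the change is held at 3.5, so a lower ρ means a larger gain over the unadjusted t-test.

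| Simulated power, imputation plus adjustment | ρ = 0.5 | ρ = 0.7 |
|---|---|---|
| Reading A, 5% imputed | about 89 to 90% | about 85 to 86% |
| Reading B, 5% imputed | about 86% | about 81% |
| Reading B, 5% imputed and 5% off drug with no benefit | about 82 to 83% | about 77% |

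**5. Break-even under reading B.** Without the imputation variance, the explained share must equal 1 − (1 − f)². That is 0.0975 for f = 0.05 and 0.19 for f = 0.10. Since the explained share is (1 − ρ)/2, break-even is ρ = 1 − 2 × 0.0975 = 0.805 and ρ = 1 − 2 × 0.19 = 0.62. The imputation variance lowers these to about 0.77 and 0.59. Simulated power at those two values is 80.6% and 80.0%.

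**6. What Table 2-2 already discloses.** At 1072 subjects it prints 64.7% for 0.5 mmol/L. The diluted differences of 0.57 and 0.54 lie between its 0.5 and 0.6 rows. Even 15% dilution, 0.6 × 0.85 = 0.51, gives 66.4% unadjusted.

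**7. Steps 3 and 4.** If the tests were independent, the chance of reaching and passing step 3 would be 0.8006 × 0.5337 = 0.427. For step 4 it would be 0.427 × 0.1545 = 0.066. With positive correlation these rise, but they cannot exceed 53.4% and 15.5%. The documents give no correlation from which to choose a value.

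**The case for a change.** The best case for acting is that the calculation is not the planned test, the discontinuation rate is stated and then left unused, and a reader cannot tell from the text what 80.1% is conditional on. For HbA1c the plan explains a conservative SD by the scarcity of data from subjects who stop treatment; for step 2 it gives no similar comment. A sentence defining 0.6 would cost nothing.

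The descriptive part of this stands: the figure is unadjusted and complete-data, and 0.6 is not defined as explicitly as it could be. The inference that power is overstated does not follow:

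- The section names the primary estimand, the FAS and the actual treatment difference. That estimand counts subjects regardless of discontinuation, and SAP section 2 repeats it for the 1-hour PPG increment.
- At the plan's rates, 5% imputed is an upper figure for withdrawal, because a withdrawer's Visit 30A meal test on randomised insulin stands in for week 16.
- Zero benefit in everyone who stops drug is an assumption. They move to a marketed product chosen by the investigator, and Protocol 3.1.3 notes that faster aspart is itself approved in several markets.
- The unadjusted losses of 4 to 10 points belong to an analysis that will not be run.

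On steps 3 and 4, Table 2-1 shows each as a two-group t-test. The plan sizes on steps 1 and 2 only and claims no joint probability. The missing word there is "marginal", a matter of labelling.

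**Conclusion.** No change follows. The 80.1% is arithmetically correct for a true primary-estimand difference of 0.6 mmol/L with SD 3.5 and 536 per arm. On that reading, the planned imputation with 5% missing costs about half a point to one point unadjusted, and the planned baseline adjustment more than recovers it over the correlations examined.

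On the on-drug reading, the planned model stays at or above 80% up to a correlation of about 0.77 with 5% imputed, and about 0.6 if a further 5% show no benefit off drug. Above those values power falls short of 80%; the lowest planned-model figure found was about 77%, at ρ = 0.7 with both losses. These results rest on equal variances at the two visits, an assumed correlation, and the plan's 10% rate. A higher rate would lower the break-even: for 15% dilution, 1 − 2 × 0.2775 = 0.445 before imputation variance.

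The documents therefore do not show that the design misses its stated power. The simple t-test omits a modest loss and a gain that is often larger, which is a fair planning simplification, and Table 2-2 already shows sensitivity beyond the diluted cases. The undefined status of 0.6 and the unlabelled step 3 and 4 columns are gaps in description. The sample size, the analysis, the testing order and every decision rule are the same whichever way they are filled.

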2.3 Primary endpoint

The primary endpoint is the change from baseline in HbA_{1c} 16 weeks after randomisation.

Primary analysis

- 1) The primary estimand will be addressed by the below primary analysis based on all subjects included in the FAS and using the in-trial observation period. Note that if subjects withdraw consent to contribute additional information or are completely lost to follow-up, missing data will occur. The primary analysis will be implemented as a statistical model using multiple imputations where the subjects without HbA_{1c} measurements at scheduled visits will have their change from baseline HbA_{1c} value(s) imputed from the available information from the treatment group the subject has been randomised to. Note that this resembles in essence a mixed model of repeated measurements analysis. Subjects without post-randomisation measurements contribute to the analysis, as the missing values will be imputed. The analysis will be implemented as follows:
 - In the first step, intermittent missing values are imputed using a Markov Chain Monte Carlo method, in order to obtain a monotone missing data pattern. This

imputation is done for each group separately and 100 copies of the dataset will be generated.

- In the second step, for each of the 100 copies of the dataset, an analysis of variance model with region and metformin use at baseline (Yes/No) as factors and baseline HbA_{1c} as covariate is fitted to the change in HbA_{1c} from baseline to week 4 for each treatment group separately. The estimated parameters, and their variances, from these models are used to impute missing values at week 4 for subjects in each treatment group, based on region, metformin use at baseline (Yes/No) and baseline HbA_{1c}.
- In the third step, for each of the 100 copies of the dataset, missing values at week 8 are imputed in the same way as for week 4. The imputations are based on an analysis of variance model with region and metformin use at baseline (Yes/No) as factors and baseline HbA_{1c} and change from baseline in HbA_{1c} at week 4 as covariates.
- This stepwise procedure is then repeated sequentially for week 12 and 16
- For each of the complete data sets, the change from baseline to week 16 is analysed using an analysis of variance model with treatment, region and metformin use at baseline (Yes/No) as factors, and baseline HbA_{1c} as a covariate.
- The estimates and standard deviations for the 100 data sets are pooled to one estimate and associated standard deviation using Rubin's formula:

$$m_{MI} = \frac{1}{100} \sum_{i=1}^{100} m_i$$

$$SD_{MI} = \sqrt{\frac{1}{100} \sum_{i=1}^{100} SD_i^2 + \left(1 + \frac{1}{100}\right) \left(\frac{1}{100 - 1}\right) \sum_{i=1}^{100} (m_i - m_{MI})^2}$$

where m_i and SD_i are the estimated means and standard deviations for the 100 copies of the dataset, and m_{MI} and SD_{MI} are the pooled estimates.

From m_{MI} and SD_{MI} , the 95% confidence interval for the treatment differences is calculated.

Non-inferiority of faster aspart will be considered confirmed if the upper boundary of the two-sided 95% confidence interval is below or equal to 0.4% or equivalent if the p-value for the one-sided test of

Statistical Analysis Plan Trial ID: NN1218-4113 UTN: U1111-1180-0636 EudraCT No.: 2016-000878-38

CONFIDENTIAL

Date: Version: Status: Page:

12 February 2019 | Novo Nordisk Final 13 of 29

 $H_0: D > 0.4\%$ against $H_A: D \le 0.4\%$,

is less than or equal to 2.5%, where D is the mean treatment difference (faster aspart minus NovoRapid[®]).

Note that as the anticipated number of subjects discontinuing treatment, but not trial is low, multiple imputations based on such subjects is not expected to be suitable.

Provided that the hierarchical testing allows, the evaluation of superiority will be based on the same statistical model, as the primary analysis 1). The associated sensitivity an alysis that follows will investigate the robustness of non-inferiority (analyses 3a and 3d) and superiority (analyses 3b and 3c) as well.

Sensitivity analyses for the primary analysis addressing the primary estimand

All sensitivity analyses for the primary analysis addressing the primary estimand will use the in-trial observation period.

- 2) First the primary analysis in 1) will be repeated, but excluding all factors except from treatment from the multiple imputation and analysis of variance models while still including baseline HbA_{1c} as a covariate. This analysis will explore the influence of the different factors.
- 3) The primary analysis approach chosen for this trial relies on the assumption that missing data is missing at random (MAR). This assumption implies that the HbA_{1c} for subjects leaving the trial, after their withdrawal, develops in a similar way as the HbA_{1c} for similar subjects that remain in the trial (not necessarily on treatment) and had similar development of HbA_{1c} before withdrawal. The MAR assumption may be questionable for subjects withdrawing at own will. Therefore the statistical model using multiple imputation will be repeated with the following alterations:
 - a) Imputations will be done from the treatment arm that the subject was randomised to and a value of 0.4% (non-inferiority margin) is added to the change from baseline in HbA_{1c} at week 16 for subjects randomised to faster aspart with an imputed value at week 16^{2} . This will serve as a sensitivity analysis for the non-inferiority analysis.
 - b) Imputations will be done from the comparator arm (NovoRapid®). This will serve as a supplementary sensitivity analysis for the superiority analysis. The imputation will be done conditional on observed information for subjects on faster aspart without a measurement at week 16 such that the treatment effect diminishes gradually (copy reference/conditional imputation). It does not rely on the MAR assumption, but

12 February 2019 | Novo Nordisk Statistical Analysis Plan Date: Trial ID: NN1218-4113 Version: CONFIDENTIAL UTN: U1111-1180-0636 Status: EudraCT No.: 2016-000878-38 Page: 14 of 29

> assumes that subjects on faster aspart without a measurement at week 16 switch to NovoRapid[®]. The analysis will use data from the in-trial observation period.

Final

- c) Imputation will be done from the comparator arm (NovoRapid[®]). This will serve as a supplementary sensitivity analysis for the superiority analysis. The imputation will be done with no regard to observed information for subjects on faster aspart without a measurement at week 16 such that the treatment effect diminishes immediately (jump to reference/unconditional imputation). It does not rely on the MAR assumption, but assumes that subjects on faster aspart without a measurement at week 16 switch to NovoRapid[®]. The analysis will use data from the in-trial observation period.
- d) A tipping point analysis based on a statistical model using multiple imputations similar to 1), using the in-trial observation period, will be made. In this analysis, observations for subjects without a measurement are imputed based on the treatment arm they were randomised to and subjects on faster aspart without a measurement are given a penalty. This is done to investigate the robustness of the conclusion in the primary analysis with respect to the MAR assumption and mimics a scenario where the HbA_{1c} of the subjects without a measurement in the faster aspart group evolve less favourably than predicted. As a first step imputations will be done without penalty assuming MAR in the treatment group. Second, the imputed values for week 16 in the faster aspart group will be added a penalty. This is done repeatedly, gradually increasing the penalty until the conclusion from the non-inferiority analysis no longer holds. This will serve as a sensitivity analysis for the noninferiority analysis and the specific value of the penalty that changes the conclusion will be used to evaluate the robustness of the conclusion of the non-inferiority analysis.

Analyses addressing the secondary estimand

All analyses addressing the secondary estimand will use the on-treatment observation period.

- 4) The secondary estimand will be analysed using the same statistical model using multiple imputations as the primary analysis in 1) except using the on-treatment observation period.
- 5) A tipping point analysis based on a statistical model using multiple imputations, similar to sensitivity analysis 3)-d except using the on-treatment observation period.
- 6) A tipping point analysis based on a statistical model using multiple imputation, similar to 5) but with the modification that subjects without a measurement that discontinued treatment due to non-eligibility (Subjects discontinuing randomised treatment prematurely due to criteria 1, 2, 3, and 4, which are defined in section 6.6 in the protocol) in the faster aspart

group will not have a penalty added to the imputed values. This analysis is motivated by the fact that data from subjects prematurely discontinuing randomised treatment due to non-eligibility can reasonably be assumed to be missing completely at random.

7) The same statistical model using multiple imputations as the analysis in 4), but using the PP analysis set and analysed using the on-treatment observation period. This analysis will investigate the situation that subjects might have deviated from the inclusion and exclusion criteria and will serve as sensitivity analysis for the non-inferiority analysis.

